2.3. Sample Size and Power Considerations

This study is powered to detect differences between REGN5713-5714-5715 and placebo on the primary endpoint of the average CSMS during birch pollen season. A sample size of 120 subjects per arm gives 90% power to detect a mean difference in average CSMS of 1.9 (30% reduction from placebo) in REGN5713-5714-5715 (mean CSMS = 4.4) and placebo (mean CSMS = 6.3),

assuming a common standard deviation in CSMS of 4.5 with a two-sample t-test at 2-sided significance level of 0.05. Assuming 20% drop out rate during the birch pollen season, the target is to randomize 150 subjects per arm.

Estimates of mean and variability of the CSMS are based on pooled estimates across several field studies for grass sublingual immunotherapy, and a 30% treatment effect relative to placebo is in line with what was observed in the phase 1b POC study for REGN5713-5714-5715.

This planned sample size (150 subjects per arm) also gives 93% power to detect a mean difference in TNSS of 0.6 (26% reduction from placebo) in REGN5713-5714-5715 (mean TNSS=1.7) and placebo (mean TNSS=2.3), assuming a common standard deviation in TNSS of 1.5 at 2-sided alpha of 0.05 using a two-sample t-test. The assumptions of TNSS endpoint are based on effects observed in the GT-08 trial of timothy grass sublingual tablet (Dahl, 2006). With the same mean for placebo and common standard deviation from GT-08 but a 30% reduction from placebo for REGN5713-5714-5715 as observed in the phase 1b POC study, the study will have a greater power.

The sample size and power calculations were performed using nQuery Advisor 7.0

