Blinded adjudication of prohibited medications will be implemented before the database lock by the study medical director, considering the type of medication, indication, timing, frequency and the potential impact of the use of the prohibited medication. The adjudication procedure will be documented.

4.4.2. **Rescue medication**

Subjects will be provided with the following medications to treat allergic symptoms during the study:

- Desloratadine 5 mg (second generation antihistamine)
- Olopatadine 1 mg/mL (antihistamine eye drop)
- Mometasone furoate 50 ug/dose (intranasal steroid)

From the time of study drug dosing throughout the birch pollen season, subjects will be asked to record their daily medication use using an e-diary, including information regarding which medications was used and the amount of the pre-specified medications that was used. Utilization of rescue medications should be initiated when subjects reach a symptoms threshold of approximately TSS \geq 4/18. Subjects will be provided with training to understand the severity of symptoms associated with a TSS \geq 4/18.

Subjects should be instructed not to utilize rescue medications in the anticipation of the birch pollen season. Subjects should also be instructed not to utilize antihistamines (ie, desloratadine or olopatadine) for 5 days before the end of study visit.

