5.6.3. Adjustment for Multiple Comparison

The following multiplicity adjustment approach, a hierarchical procedure, will be used to control overall Type-1 error rate at 0.05 for the primary endpoint and the secondary endpoints. Each hypothesis will be formally tested only if the preceding one is significant at the 2-sided 0.05 significance level. The hierarchical testing order is shown as follows.

- 1. **Primary endpoint**: Daily CSMS, averaged over the duration of the birch pollen season, in subjects who receive a single dose of REGN5713-5714-5715 versus placebo
- 2. TNSS, averaged over the duration of the birch pollen season, in subjects who receive a single dose of REGN5713-5714-5715 versus placebo
- 3. TSS, averaged over the duration of the birch pollen season, in subjects who receive a single dose of REGN5713-5714-5715 versus placebo
- 4. Change from baseline to the end of study in birch SPT mean wheal diameter in subjects who receive a single dose of REGN5713-5714-5715 versus placebo
- 5. Percent change from baseline to the end of study in birch SPT mean wheal diameter in subjects who receive a single dose of REGN5713-5714-5715 versus placebo
- 6. TOSS, averaged over the duration of the birch pollen season, in subjects who receive a single dose of REGN5713-5714-5715 versus placebo
- 7. DMS, averaged over the duration of the birch pollen season, in subjects who receive a single dose of REGN5713-5714-5715 versus placebo

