6.4. Analysis Visit Windows

Data analyzed by-visit-analysis (efficacy [excluding daily diary data], laboratory data, vital sign) will be summarized by the study scheduled visits described in the study protocol and SAP "Schedule of Event".

The analysis visit windows are created per study Schedule of Events (SOE) table for each parameter and will be applied if the data from study scheduled visits are unavailable. The following general rules will be applied to unscheduled visit and/or early termination (ET) visit mapping for each parameter.

1. If ET visit falls in an analysis window which already has non-missing observed value of this parameter from the scheduled visit, ET will be mapped to the next scheduled visit.

CONFIDENTIAL

Page 39 of 56

- 2. If both ET visit and unscheduled visit of the same parameter are available in the same analysis visit window, only ET visit will be mapped.
- 3. If multiple unscheduled visits of the same parameter are available in the same analysis visit window, the unscheduled visis will be mapped using the following rules:
 - a. The closest unscheduled visit from the target day will be selected
 - b. If multiple unscheduled visits exist on the same day, the first unscheduled visit will be used.
- 4. If mapping distance is greater than 4 weeks, the unscheduled visit will not be mapped.

Unscheduled visits and early termination (ET) visit will be mapped per the following analysis visit windows based on the study day/visit of each parameter.

Visit from SOE	Target Study Day*	PFASQ, SPT	PGI-S
Baseline	1	≤1	≤ 1
Visit 5	57		[2, 85]
Visit 7 (EOS)	113	≥ 2	≥ 86

Analysis Visit Window for Efficacy Endpoints

*Study days are calculated from the day of 1^{st} injection. Study day = (date of assessment -1^{st} injection date +1) when date of assessment $\ge 1^{st}$ injection date; otherwise study day = (date of assessment -1^{st} injection date). If subject never received any dose of study drug, randomization date will be used in the place of 1^{st} injection date.

Visit from SOE	Target Study Day*	Vital Sign	Physical Exam	Laboratory#, PK	ADA	Serum total IgE, Serum sIgE for birch pollen and Bet v 1 and other regional or relevant allergens, Serum sIgE for concomitant and homologous allergens
Baseline	1	≤ 1	≤ 1	≤ 1	≤ 1	≤ 1
Visit 5	57	≥2		[2, 85]		[2, 85]
Visit 7 (EOS)	113		≥2	≥86	≥2	≥86

Analysis Visit Window for Safety and Biomarkers

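### The SAP keeps end-of-study and early-termination skin prick tests taken within 5 days of rescue antihistamine, and leaves unclear whether its 4-week mapping limit covers early-termination visits

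*SAP*

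**What the plan says.** **Endpoint.** SAP 5.6.3 places "Change from baseline to the end of study in birch SPT mean wheal diameter in subjects" at step 4 of the hierarchy and the percent change at step 5, ahead of TOSS and DMS. SAP 10.1.1 lists no supportive or sensitivity analysis for either.

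**Medication before the test.** SAP 4.4.2 (and protocol 8.2) states: "Subjects should also be instructed not to utilize antihistamines (ie, desloratadine or olopatadine) for 5 days before the end of study visit". Protocol 8.9.1 and SAP 4.4.1 list both drugs as prohibited in that period. Before screening, when the baseline SPT is done, protocol 8.9.1 requires 5 days without second-generation antihistamines and 3 days without first-generation ones.

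**Analysis rule.** SAP 5.6.2, which covers all secondary efficacy variables, uses data after rescue and sets data to missing only under Table 2. Table 2 names systemic steroids and Type 2 biologics. The blinded adjudication in SAP 4.4.1 considers timing, but no data rule for antihistamines follows from it.

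**Visit mapping.** SAP 6.4 applies when the scheduled value is unavailable: "Unscheduled visits and early termination (ET) visit will be mapped per the following analysis visit windows based on the study day/visit of each parameter". The efficacy row reads "Visit 7 (EOS) 113 ≥ 2 ≥ 86", so the SPT window for Visit 7 opens on day 2. Rule 4 says "If mapping distance is greater than 4 weeks, the unscheduled visit will not be mapped". The lead-in says "The following general rules will be applied to unscheduled visit and/or early termination (ET) visit mapping for each parameter". The schedule of events marks SPT in the combined EOS/ET column and not in the unscheduled column.

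**The concern.** The baseline wheal is measured after an antihistamine-free period, while the follow-up wheal may be measured shortly after rescue use and still be kept. If an antihistamine shrinks the wheal, which is the natural reason for the 5-day restriction, a follow-up test inside that period shows a reduction that is not due to study drug. Placebo subjects are expected to use more rescue and have larger wheals left to suppress, so the difference between arms should shrink. The gap applies to on-time end-of-study tests as well as ET tests. ET tests are the more exposed, because withdrawal is assumed to occur in season and no passage says how the 5-day restriction applies to an ET visit.

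The second question is timing. Rule 4 names only unscheduled visits, by which SPTs are not scheduled to arise. Rules 1 and 2 name ET separately. Read literally, an ET test has no distance limit. Read with the lead-in, it does. The two readings give different data sets for two alpha-controlled endpoints, and the choice would be left to programming.

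**Working it through.** **1. The plan's own figures.** The documents give no power, SD or assumed effect for SPT in this trial. The related figure is dropout: SAP 2.3 has 120 evaluable per arm, "Assuming 20% drop out rate during the birch pollen season", and randomizes 150. Check: 120/(1 − 0.20) = 150, so 30 per arm are lost. Power at 120 per arm for a difference of 1.9 with SD 4.5 is 0.903 by t-test, which reproduces the stated 90%. The 30 per arm is an upper bound on ET skin tests, because protocol 9.1.2 only asks withdrawn subjects to return.

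**2. Mapping distance.**
- Window as written: 113 − 2 = 111 days.
- If the 4-week limit covered ET: earliest usable day 113 − 28 = 85.
- In practice: SPT is analysed on the FAS, which needs an in-season diary entry (SAP 3.1). Randomization is about 2 weeks before the season (SAP 10.2, footnote 3), so the earliest ET test analysed is at about day 15, and 113 − 15 = 98 days.

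**3. Size of the timing effect.** Protocol 1.3 gives placebo-adjusted phase 1b SPT changes of −72.39% (day 8), −65.61% (day 29), −77.90% (day 57) and −73.56% (day 113). With a share f of each arm tested at day d instead of day 113, shift = f × (effect at d − effect at 113). At f = 0.20:

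| ET tests all at | Shift (points) |
|---|---|
| day 8 | 0.20 × 1.17 = +0.2 |
| day 29 | 0.20 × 7.95 = +1.6 |
| day 57 | 0.20 × (−4.34) = −0.9 |

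These figures are areas under the curve from a titration SPT, not the trial's endpoint.

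**4. Size of the antihistamine effect.** The inputs below are assumptions, apart from the −73.56%:
- f: ET share of each arm, 10–20%.
- pP and pA: share of ET tests with recent antihistamine, placebo 35–100% and active 0–50%.
- s: wheal suppression, 30–100%.
- Placebo change without antihistamine: 0. Active: −73.56%, leaving 26.44% of the wheal.

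Placebo mean = −100·f·pP·s. Active mean = −73.56 − 26.44·f·pA·s. Shift in the difference = f·s·(100·pP − 26.44·pA).

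| f | pP | pA | s | Shift (points) |
|---|---|---|---|---|
| 0.10 | 0.35 | 0.50 | 0.30 | 0.03 × (35 − 13.22) = +0.7 |
| 0.20 | 0.50 | 0.35 | 0.60 | 0.12 × (50 − 9.25) = +4.9 |
| 0.20 | 0.80 | 0.40 | 0.60 | 0.12 × (80 − 10.58) = +8.3 |
| 0.20 | 1.00 | 0 | 1.00 | 0.20 × 100 = +20.0 |

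A positive shift is toward no effect. With a true effect this large, the sign reverses only if pA exceeds 100/26.44 = 3.8 times pP. The range counts ET tests only; on-time tests inside the restriction would add to it.

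**5. Power and Type I error.** At the extreme, the effect becomes −73.56 + 20 = −53.56%. With 150 per arm and an assumed SD of 30 to 80 points, t-test power stays above 0.999. Under no SPT effect (10,000 simulated trials, 150 per arm, f = 0.20, s = 0.60, assumed SD 40), false superiority of active, nominally 2.5%, is:

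| Recent use, placebo / active | False superiority |
|---|---|
| 50% / 50% | 2.4% |
| 50% / 35% | 1.1% |
| 80% / 40% | 0.2% |
| 40% / 80% | 16% |

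Only the last row exceeds nominal. It needs rescue use to be much higher on active, the reverse of the trial's hypothesis.

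**The case against.** **Keeping the values follows a stated strategy.** SAP 5.6.2 uses data after rescue, and SAP 1.2.4 describes a treatment policy for prohibited drugs other than systemic steroids and Type 2 biologics. This stands in part. It is a defensible estimand, but SAP 1.2.4 and Table 1 were written for the diary-based primary endpoint. Rescue use is part of what CSMS measures, whereas for a skin test it disturbs the measurement. No passage says the SPT endpoint is meant to include it.

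**Exclusion has its own bias.** Dropping tests after recent antihistamine conditions on a post-randomization event related to treatment, and would remove symptomatic placebo subjects preferentially. This stands, and is why neither analysis should be shown alone. A withdrawn subject's diary may also stop before the ET visit; concomitant medications recorded at that visit fill only part of the gap.

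**A hard 4-week limit gains little.** SPT is scheduled once after baseline, so dropping ET tests before day 85 leaves those subjects with no post-baseline value. This stands, and the limit belongs in a sensitivity analysis.

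**Stronger readings.** A reader might infer that ET tests are taken before the drug works. The documents point the other way: the phase 1b effect was already −72.39% at day 8, and subjects who leave before the season are not in the FAS. A reader might also infer that false positives are inflated, or that the gate to TOSS and DMS is at risk. Step 5 of the check supports neither under the expected pattern of rescue use. Nor is a distance limit plainly absent for ET, since the lead-in to the rules names ET visits.

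**Conclusion.** The SAP retains SPT values taken inside the documents' own 5-day antihistamine restriction, at end of study and at ET, in hierarchy steps 4 and 5. The most plausible consequence is an attenuated estimate. The amount cannot be fixed from the documents: the 0.7 to 20 points (up to 20/73.56 = 27% of the phase 1b effect) rests on assumed ET shares, rescue use and wheal suppression. The upper end needs every placebo ET test, and no active one, to follow recent use with complete suppression. No Type I error inflation or material power loss is shown, so the problem lies in the estimate and its definition rather than in the test.

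The scope of rule 4 is ambiguous. On the phase 1b time course the resulting timing shift is at most about 1.6 points with 20% ET tests in each arm, subject to that time course being a different SPT measure. Both matters merit a SAP clarification; neither threatens the trial's main conclusion.

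**What to change.** Make these changes before database lock and code breaking.

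1. Pre-specify that an SPT value, at end of study or ET, is not valid for the SPT analysis when the e-diary or concomitant-medication record shows desloratadine or olopatadine in the preceding 5 days. Report the all-values analysis beside it. If the sponsor prefers to keep the rescue rule of SAP 5.6.2 as the main analysis, reverse the order. State which of the two is tested at steps 4 and 5, and how a missing 5-day look-back is treated.
2. State in SAP 6.4 whether rule 4 covers ET visits, and add a sensitivity analysis using only SPTs within 4 weeks of day 113.
3. Reconcile protocol 8.2, 8.9.1 and 9.1.2 on how the 5-day restriction applies to an ET visit.

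The cost is a few sentences and additional tables from records the trial already collects. Some SPT values are lost from one analysis, and the exclusion depends on a post-randomization event, which is the reason to show both results.

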6.5. Statistical Technical Issues

None.

Regeneron Pharmaceuticals, Inc. Statistical Analysis Plan

7. INTERIM ANALYSIS

No formal interim analysis will be conducted.

Regeneron Pharmaceuticals, Inc. Statistical Analysis Plan

10. APPENDIX

10.1. Summary of Statistical Analyses

10.1.1. Summary of Efficacy Analyses

Endpoint	Analysis Populations	Primary Statistical Method	Supportive/Sensitive Statistical Method	Subgroup Analysis	Other Analyses
Primary Endpoints				·	
Daily CSMS, averaged over the duration of the birch pollen season	FAS	Linear-mixed effect model	N/A	Yes	Plot
Secondary Endpoints					
TSS, TNSS and TOSS averaged over the duration of the birch pollen season	FAS	Linear-mixed effect model	N/A	No	Plot
DMS, averaged over the duration of the birch pollen season	FAS	Linear mixed effect model	N/A	No	Plot
Change and percent change from baseline to the end of study in birch SPT mean wheal diameter	FAS	Linear mixed effect model	N/A	No	Plot
The number of "well days" in each of the treatment groups,	FAS	Linear mixed effect model	N/A	No	Plot

10.1.2. Summary of Safety Analyses

Endpoint	Analysis Populations	Statistical Method	Supportive Analysis	Subgroup Analysis	Other Analyses
Adverse Events	SAF	Descriptive statistics and model-based analyses	No	Yes, for selected AE summary	No
Laboratory Measures	SAF	Descriptive Statistics	No	No	No
Vital sign	SAF	Descriptive Statistics	No	No	No

10.2. Schedule of Time and Events

Table 3: Schedule of Events

	SCREENING PERIOD	TREATMENT P	ERIOD	F	OLLOW-	UP PER	IOD	
Study Procedure	Screening Visit 1 ¹	Randomization Visit 2 ²⁻⁴	Visit 3 Tel.	Visit 4 Tel.	Visit 5 ³	Visit 6 Tel.	EOS/ET Visit 7 ³	Unscheduled visit
Day	-84 to -7	1 ³	2	28 ³	57 ³	85	113 ³	
Window (Days)	+7	± 3		±7	±14	±14	±14	
Inclusion/exclusion ²	X	Х	[[
Informed consent	Х							
Medical history	X ⁴							
Demographics	Х							
SPT for birch and birch homologous allergens and select regional or relevant allergens ¹	Х						Х	
Standard regional SPT for birch and other common allergens ¹	Х							
FSH (in postmenopausal women)	X							
Treatment								
Randomization ²		Х						
Study drug administration ²		Х						
Efficacy								
E-diary and rescue medications dispensation/return ⁵		Х					Х	
TNSS ⁶			Dai	ly via e-d	iary			
TOSS ⁶			Dai	ly via e-d	iary			
DMS ⁶			Dai	ly via e-d	iary			
ACQ-5 (in subjects with asthma) ⁷			Wee	kly via e-	diary			Х
$RQLQ (S)^8$			Wee	kly via e-	diary			Х
PFASQ ⁹		Х					Х	
PGI-S ¹⁰		Х			Х		Х	
Safety								
Vital signs ¹¹	Х	X^{11}			Х			Х
Physical examination ¹²	Х	Х					Х	Х
ECG	Х							
AEs	Х	Х	Х	Х	Х	Х	Х	Х
Height	X							
Weight	X							
Concomitant medications	Х	Х	Х	Х	X	Х	X	Х

Regeneron Pharmaceuticals, Inc. Statistical Analysis Plan

	SCREENING PERIOD	TREATMENT P	ERIOD	F	OLLOW-	UP PER	IOD	
Study Procedure	Screening Visit	Randomization Visit 2 ²⁻⁴	Visit 3 Tel.	Visit 4 Tel.	Visit 5 ³	Visit 6 Tel.	EOS/ET Visit 7 ³	Unscheduled visit
Day	-84 to -7	13	2	28 ³	5 7 ³	85	113 ³	
Window (Days)	+7	±3		±7	±14	±14	±14	
Spirometry	X4	X						X
Laboratory Testing								
Hematology	X ⁴				X		X	X
Blood chemistry	X^4				X	_	Х	X
Pregnancy test, urine (in WOCBP) ¹³		X ¹³		X ¹³	X	X ¹³	X	X
Pregnancy test, serum (in WOCBP) ¹³	Х							X
Urinalysis	Х							Х
Serum total IgE		Х			Х		Х	
Serum sIgE for birch pollen and Bet v 1 and other	Х	X			X		X	X
Serum sIgE for concomitant and homologous allergens		Х			X		X	
Interference assay, serum		Х						
Pharmacokinetics and Immunogenicity			·	.	-			
PK ¹⁴		X ¹⁴			X		X	X
ADA ¹⁴		X ¹⁴					X	X
Biomarkers and Pharmacogenomics								
FBR samples, serum and plasma (optional) ¹⁵		X			X		Х	
Genomic DNA sample (optional) ¹⁶		X ¹⁶						
ACQ-5=asthma control questionnaire-5; ADA=anti- study; ET=early termination; FBR=future biomedica S=patient global impression of severity; PK=pharma immunoglobulin E; SPT=skin prick test; Tel=telepho	drug antibody; AE= l research; FSH=fo cokinetics; RQLQ one; TNSS=total na	=adverse event; DMS Ilicle stimulating hor (S)=standardized rhin Isal symptom score; ?	=daily me mone; PF noconjunct FOSS=tota	dication s ASQ=poll tivitis qua ll ocular s	core; ECC en food al lity of life ymptom s	G=electro lergy syn question core; WO	cardiogram; nptom quest naire; sIgE= OCBP=wom(EOS=end of ionnaire; PGI- allergen-specific en of childbearing
potential.								

Footnotes for the Schedule of Events Table

- 1. Screening SPT for birch, birch homologous trees, and other common allergens will be performed as described in the study manual. Skin prick test for birch should be performed prior to other screening assessments. If screening SPT for birch is negative (ie, mean wheal diameter <5 mm greater than a negative control), then other screening visit procedures do not need to be performed as the subject will have failed screening (refer to Protocol Section 7.2.1 Inclusion Criteria, #3).
- 2. Randomization may occur within 1 day prior to study drug administration. All safety assessments performed at screening must be normal and checked against the inclusion/exclusion criteria prior to study drug administration.
- 3. The timing of in-clinic visits may vary for each study site, depending on the start, peak, and end dates of the local birch pollen season (as determined by local pollen counts; refer to Protocol Section 9.2.2). The randomization visit will be scheduled approximately 2 weeks before the start of birch pollen season, and the end of study (EOS) visit approximately 16 weeks after the randomization visit (depending on the duration of the local birch pollen season). In addition, visit 5 will be scheduled to occur within 2 weeks of the anticipated local peak of the birch pollen season.
- 4. If randomization occurs >60 days after the screening visit, medical history, blood chemistry, hematology, and spirometry must be repeated prior to randomization.
- 5. E-diary and rescue medications will be dispensed at the randomization visit. E-diary and any unused rescue medications will be returned at the EOS visit. Refer to Protocol Section 8.2 for more information on rescue treatments.
- 6. TNSS, TOSS, and DMS will be recorded daily via e-diary, starting at the randomization visit until EOS. Refer to Protocol Section 9.2.4.1, 9.4.2.2 and 9.4.2.4 for procedural details.
- 7. In asthmatic subjects, ACQ-5 scores will be recorded weekly via e-diary, starting from the randomization visit until EOS. Refer to Protocol Section 9.2.4.6 for procedural details.
- 8. In all subjects, RQLQ (S) scores will be recorded weekly via e-diary starting from the randomization visit until EOS. Refer to Protocol Section 9.2.4.7 for procedural details. In asthmatic subjects, the weekly RQLQ (S) and ACQ-5 assessments may be performed on the same day.
- 9. Refer to for Protocol Section 9.2.4.8 procedural details.
- 10. Refer to for Protocol Section 9.2.4.9 procedural details.
- 11. Vital signs include systolic and diastolic blood pressure, respiratory rate and heart rate. Vital signs will be collected in a seated position. At the randomization visit, vital signs are taken prior to PK blood draw, prior to study drug administration, and at 2 hours (±10 min) after completion of the injection.
- 12. A full physical exam must be performed at screening, at baseline, and at EOS. A limited physical exam will be done at remaining visits depending on presentation of the subject.
- 13. If the urine pregnancy test is positive, the site must perform a serum pregnancy test for confirmation. At the randomization visit, if a serum pregnancy test must be performed,

CONFIDENTIAL

Page 52 of 56

VV-RIM-00163457-1.0 Approved - 04 Aug 2021 GMT-5:00

study drug cannot be administered unless the serum pregnancy test is negative. Urine pregnancy test can be performed on day -1 of the visit at the investigator's discretion.

At-home pregnancy testing: WOCBP will be provided with urine pregnancy tests for at-home testing prior to visits 4 and 6. Study sites will collect the results by telephone at these visits. If the urine pregnancy test is positive, the site must perform a serum pregnancy test for confirmation.

- 14. PK and ADA samples are to be collected prior to study drug administration. In the event of suspected SAEs, such as anaphylaxis or hypersensitivity, additional samples for PK and ADA analyses may be collected as close to the event as practically possible.
- 15. Refer to Protocol Section 9.2.11.
- 16. Genomic analysis is optional for all subjects enrolling in the study. One DNA sample is to be collected at the randomization visit, but if this sample collection was omitted at baseline, it can be collected at any subsequent visit. Refer to Protocol Section 9.2.12.

Parameter	PCSV	Comments
Clinical Chemis	stry	
ALT*	>3 and \leq 5 ULN and baseline \leq 3 ULN* >5 and \leq 10 ULN and baseline \leq 5 ULN >10 and \leq 20 ULN and baseline \leq 10 ULN >20 ULN and baseline \leq 20 ULN	Enzymes activities must be expressed in ULN, not in IU/L. Concept paper on DILI – FDA draft Guidance Oct 2007. Each category is calculated independently. * At least one level is required; multiple levels are optional for phase 2/3 studies. If it is desirable to get the distribution across the different PCSV levels, additional shift table on ≤ 3 , ≥ 3 to ≤ 5 , ≥ 5 to ≤ 10 , ≥ 10 to ≤ 20 , and ≥ 20 category for baseline vs. post baseline may be provided
AST*	>3 and \leq 5 ULN and baseline \leq 3 ULN* >5 and \leq 10 ULN and baseline \leq 5 ULN >10 and \leq 20 ULN and baseline \leq 10 ULN >20 ULN and baseline \leq 20 ULN	Enzymes activities must be expressed in ULN, not in IU/L. Concept paper on DILI – FDA draft Guidance Oct 2007. Each category is calculated independently. * At least one level is required, multiple levels are optional for phase 2/3 studies. If it is desirable to get the distribution across the different PCSV levels, additional shift table on ≤ 3 , ≥ 3 to ≤ 5 , ≥ 5 to ≤ 10 , ≥ 10 to ≤ 20 , and ≥ 20 category for baseline vs. post baseline may be provided
Alkaline	>1.5 ULN and baseline ≤ 1.5	Enzyme activity must be expressed in ULN, not in IU/L.
Total Bilirubin*	 >1.5 and ≤ 2 ULN and baseline ≤ 1.5 ULN* >2 ULN and baseline ≤ 2.0 ULN 	Must be expressed in ULN, not in μ mol/L or mg/L. Categories are cumulative. Concept paper on DILI – FDA draft Guidance Oct 2007. * At least one level is required, multiple levels are optional for phase 2/3 studies. If it is desirable to get the distribution of significant level, additional shift table on ≤ 1.5 , >1.5 to ≤ 2.0 and > 2.0 category for baseline vs. post baseline may be provided
(ALT or AST) and Total Bilirubin	((ALT >3 ULN or AST>3 ULN) and TBILI>2 ULN) and baseline ((ALT ≤3 ULN and AST ≤3 ULN) or TBILI ≤2 ULN))	Concept paper on DILI – FDA draft Guidance Oct 2007.
Creatinine	≥150 µmol/L (Adults) and baseline < 150 µmol/L ≥30% change from baseline and <100% change from baseline ≥100% change from baseline	Benichou C., 1994. 3 independent criteria
Uric Acid	<120 µmol/L and ≥ 120 µmol/L at baseline >408 µmol/Land ≤ 408 µmol/L at baseline	Harrison- Principles of Internal Medicine 17th Ed., 2008. Two independent criteria
Blood Urea Nitrogen (BUN)	\geq 17 mmol/L and <17 mmol/L at baseline	Two independent criteria
Chloride	<pre><80 mmol/L and baseline \geq 80 mmol/L >115 mmol/L and baseline \leq115 mmol/L</pre>	Two independent criteria
Sodium	≤129 mmol/L and baseline > 129 mmol/L ≥160 mmol/L and baseline < 160 mmol/L	Two independent criteria

